11.7. The Level of Statistical Significance

A nominal significance level of 5% will be used; however, results will be interpreted based on their 95% confidence intervals rather than using a rigid threshold approach.

11.8. Procedure for Accounting for Missing, Unused, and Spurious Data

Each analysis will be restricted to complete cases for the outcomes and exposures considered for that analysis. Missing assay data is expected to be extremely rare, as study workers will oversee the participant self-swabbing of nose and throat, participant capillary blood draw, and ask the specific additional questions at the home visit. From protocol v16.0, samples will be returned predominantly by post, so missing data may increase somewhat, but postal return has been used successfully by other research studies such as REACT and Biobank without substantial amounts of missing data. The RT-PCR and ePCR tests for virus have been used as a diagnostic throughout the pandemic and hence have extremely high performance. Sufficient sera will be obtained to re-run the immunological assays in case of initial assay failure. For similar reasons we do not anticipate that spurious data will be obtained.

Regular checks for data quality will be run on the small amount of predominantly self-reported data collected (see section 9.6.1). Standard range checks and plausibility checks will be run on all data fields as part of routine data processing for interim analyses. For participants agreeing to serial sampling, consistency between visits will also be checked. Given the short-time scales of the study visits, last observation carried forward and backward will be used to impute any missing data.

Standard inverse probability weighting methods or post-stratification will be used to weight observed data back to a representative UK population, based on response to the initial ONS letter in adults originally targeted, their characteristics compared with those to whom the original invite to participate in the ONS and NISRA surveys, and those characteristics vs the general UK population.

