These cross-sectional surveys will be repeated over time, recruiting new households each week, following standard sampling methods (for example as employed in the Labour Force Survey) to ensure that the study represents the UK population and can estimate reliably prevalence over time of symptomatic and asymptomatic infection and immunity (as assessed by various antibody profiles) (Figure 1). In each cross-sectional survey, up to protocol v15.0 study participants who provide additional optional consent/assent will undergo repeated serial sampling at 1, 2, 3 and 4 weeks (approximately 1 month) after their enrolment visit (week 0) to assess incidence of new infection, viral clearance and changes over time in immunity. If further additional consent is given, this will then be further repeated at month 2 and every month thereafter from their first study visit to assess these outcomes over the longer term. Up to protocol v15.0, the choice of participating once at enrolment, weekly for the first month, or weekly for the first month and then monthly will be made at the enrolment visit; participants will not be offered the option to extend if they initially choose weekly visits for one month only. Over 95% of participants offered these options through to protocol v15.0 chose to have repeated monthly visits over the longer term, and a number of those who initially chose 1 or 5 visits requested to then extend their participation (which was not possible under the approved protocol). Therefore from protocol v16.0, we will ask everyone joining the study to have study assessments every week for the first month and then every month until the study ends. Participants are free to withdraw at any time.

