Study worker visits will continue to be scheduled under protocol v16.0 for all participants who have not yet received their invitation to continue the study under the new approach (up to one home visit will be scheduled after this invitation, but if the household does not attend, no further home visits will be scheduled). Study visits will stop as soon as these final scheduled visit dates have passed.

Monthly visits will initially be implemented as 31 days apart, but given substantial uncertainty in the percentage of testing windows that will be completed under the new approach, this schedule may be extended by up to 5 days (to 36 days) or shortened by up to 3 days (to 28 days) in order to achieve the overall sample targets with the (unknown) number of participants who choose to opt in to the new approach. This does not impact analysis as the key objectives relate to rates over calendar time, not by time since participants joined the study.

[figure not shown]

Figure 4 Illustration of the impact of staged approach to transition a theoretical 100,000 participants on the number of completed tests per week

9.4.4.1. Collection of quantitative and qualitative data for process evaluation during the transition

The goal of the quantitative and qualitative process evaluation 1 is to test how the new approach to delivery was actually used and received in practice. Process evaluation will include surveys offered to all participants invited to and opting to continue the study in Stages 1 and 2, and interviews in a sub-sample of those from Stage 1. Those newly recruited after the temporary pause in recruitment during the transition to the new approach will also be invited to similar quantitative and qualitative feedback.

Quantitative process evaluation

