- Working status (employed, not working, retired, student etc) and work location (at home, outside of home etc), including number of days per week usually spent working outside the home or at school/nursery, and mode of transport to get to work/school/nursery
- Healthcare and social care contacts including currently working in health/social care in roles which primarily directly interact with patients/residents/clients or not, recently visited hospital or residential/nursing care home
- Contacts with other individuals inside the household (eg social distancing within the household) and outside the household, including through work, school/nursery, shopping, exercise etc including duration and number of individuals, how easy they find it to maintain social distancing and use of face coverings or masks
- Do they have long-term health problems, and do these limit their activities?
- Current smoking status
- Have they recently travelled abroad? If yes, to which countries?
- Have they received or been offered a vaccine against COVID-19? If yes, type, number of doses, dates.
- Have they received a vaccine against influenza? If yes, date.
- Do they think/know they have been infected by COVID-19? Yes/No
 - If yes, date first symptoms and what symptoms (yes/no for each of fever (including high temperature), muscle ache (myalgia), fatigue, sore throat, cough, shortness of breath (dyspnea), chest pain, headache, nausea/vomiting, abdominal pain, diarrhoea, loss of taste, loss of smell, trouble sleeping, loss of appetite/eating less than usual, runny nose/sneezing, noisy breathing (wheezing), chest pain, palpitations, vertigo/dizziness, memory loss/confusion, difficulty concentrating, worry/anxiety, low mood/not enjoying anything, other symptoms)
 - \circ If yes, did they contact the NHS about this (suspected) COVID-19 infection? Yes/No
 - If yes, were they tested? Yes/No
 - If tested, were they positive/negative/test failed/results not yet received?
 - If yes, were they hospitalised Yes/No?
 - If yes, do they think that they are suffering from "long COVID" and with what symptoms?
 How is this limiting their activities?

Household postcode (required at the level of outward portion and first number of the inward portion for geospatial analyses) will be available from the original ONS or NISRA survey or the address list from which the household was sampled. However, full address will also be confirmed against the household

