9.8. Subsequent Visits

Households from which one or more participants consent to serial sampling (up to protocol v15.0; from protocol v16.0 all households) will have assessments approximately 1, 2, 3, and 4 weeks later, and then (depending on consent up to protocol v15.0, Figure 2) two months after the enrolment visit and every month thereafter through to the end of the study. Up to protocol v16.0, to allow for participant convenience and study workers availability, visits should occur within equidistant windows around scheduled study timepoints, that is within a ±3 day window for the first three weekly visits, within a window of [-3,+16] days around the week 4 visit, or within a ±15 day window around the visits from months 2 onwards. One home visit will be made to each household at each of these timepoints, and all consenting participants in the household at the time of the home visit will be included – additional visits will not be made if one or more participant happens not to be present at the time of an individual visit. Such participants may however be included at subsequent visits. From protocol v16.0, study assessments will be scheduled from the first study assessment under the new mode of delivery (see Table 2B), with the same windows. Participants will have the option to opt out of any assessment. Windows for completion will be 7 days from the start of the assessment window for weekly visits and 14 days from the start of the assessment window for monthly visits. Any questionnaires or samples returned after this will be used in analysis, but participants will not receive compensation if the questionnaire has been completed outside these windows or if the participant states that they have not performed one or more of the swab or the blood test (the latter if doing blood tests), in order to promote participants remaining as close to their scheduled monthly assessments as possible. Participants will continue to receive compensation if they state that they have taken a swab/blood but the sample(s) do not arrive at the consolidation hub three times (non-consecutive). On the third occasion, IQVIA will contact the

Clinical Research Protocol Template version 15.0

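### Section 11.8 imputes any missing data by carrying values both ways, with no variable list, maximum gap or order against the complete-case rule, for a reason that fits only the weekly visits

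*Protocol*

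**What the plan says.** Section 11.8 contains two rules. It opens with "Each analysis will be restricted to complete cases for the outcomes and exposures considered for that analysis". Its second paragraph deals with quality checks on the mainly self-reported questionnaire data and consistency between serial visits, and ends: "Given the short-time scales of the study visits", "last observation carried forward and backward will be used to impute any missing data". It does not say which variables are meant, how far a value may travel, or which rule is applied first.

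The spacing of visits is set elsewhere. Section 7 has "study assessments every week for the first month and then every month until the study ends". Section 9.8 allows home visits "within a ±15 day window around the visits from months 2 onwards". Section 9.4.4 says "Monthly visits will initially be implemented as 31 days apart" from v16.0, with permission to shorten to 28 or lengthen to 36 days. Section 7 lets participants miss individual visits.

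Section 9.6.1 lists the items at risk: symptoms on the day or since the last visit, current self-isolation, recent contacts, long COVID, and "Have they received or been offered a vaccine against COVID-19", the last with type, doses and dates. Section 11.1 states that no formal statistical analysis plan exists, so Section 11.8 is the operative rule in the document at hand.

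**The concern.** A rule that covers all missing data, in both directions and without limit, treats sex and today's cough alike. Carrying is harmless for a fixed characteristic and reasonable over short gaps for one that changes slowly. It is wrong for a state that comes and goes within days. Backward carry adds a second problem, because a later value then defines an earlier exposure.

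Two objectives in Section 6 are exposed. The primary objective concerns symptomatic and asymptomatic infection, so a carried symptom value can move a positive swab from one group to the other. The exploratory objectives compare infection by vaccination status and time since vaccination, and backward carry of status would count unvaccinated time as vaccinated. Filled values would also enter the models as if observed. Finally, two analysts following Section 11.8 could build different datasets, depending on which rule they apply first and to which variables.

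**Working it through.** The plan gives no figure for this rule, so there is none to reproduce. The check is whether the stated reason fits the protocol's own schedule, and whether the rule agrees with the rest of the document.

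**Step 1: inputs.**
- Home visits (Section 9.8): ±3 days for weeks 1 to 3, -3 to +16 days for week 4, ±15 days from month 2.
- From v16.0 (Sections 9.4.4 and 9.8): 31-day interval, adjustable from 28 to 36, with 14 days to complete a monthly assessment.
- Swab look-back for the primary outcome (Section 6, repeated in Section 11.2): two weeks.
- A month is taken as 28 to 31 days for home visits.

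**Step 2: longest gap between neighbouring observations in the weekly phase (home visits).**
- Week 1 to 2, or 2 to 3: 7 + 3 + 3 = 13 days.
- Week 3 to 4: 7 + 3 + 16 = 26 days.

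**Step 3: longest gap in the monthly phase, home visits.**
- No visit missed, interval + 15 + 15: 28 + 30 = 58; 31 + 30 = 61 days.
- One visit missed, 2 × interval + 30: 56 + 30 = 86; 62 + 30 = 92 days.

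**Step 4: longest gap in the monthly phase, from v16.0.**
- No visit missed, interval + 14: 28 + 14 = 42; 31 + 14 = 45; 36 + 14 = 50 days.
- One visit missed, 2 × interval + 14: 56 + 14 = 70; 62 + 14 = 76; 72 + 14 = 86 days.
- Section 9.8 also keeps late returns in the analysis, so these are not strict upper limits.

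**Step 5: compare.** Only the early weekly gaps stay within 14 days. The shortest nominal monthly interval from v16.0, 28 days, is already twice the two-week look-back. The stated reason therefore fits the weekly phase and fails for the remainder of follow-up.

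**Step 6: set the rule against each type of item.**
- Sex, ethnicity, date of birth: fixed, so two-way carry is sound. Section 9.7 allows baseline characteristics missed in error to be collected later, which backward carry suits.
- Occupation, working status, smoking, long-term conditions: slow to change. Section 9.6.1 asks only for changes at follow-up where relevant, which forward carry suits.
- Symptoms, self-isolation, recent contacts: tied to the day or a recent period. A value from a month or more away describes a different episode.
- Vaccination, long COVID: they start at a point in time. Backward carry of status labels time before that point as exposed.
- Swab result: carrying it a month or more contradicts the two-week look-back.

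**Step 7: size.** The protocol gives no item-level missingness, no rate of change for these items and no share of records that would be filled. The amount of misclassification cannot be derived from it.

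**The case against.** The strongest defence is that the two rules need not collide. They can run in sequence: fill what may be filled, then drop records still incomplete on outcome or exposure. The position of the carry sentence, at the end of a paragraph on questionnaire data, suggests that it was never aimed at assay results. That stands. A reader might infer a strict logical contradiction, but what the text shows is an unstated order and scope.

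A reader might also infer that the primary swab estimates are built on carried results. The documents do not support this. Section 6 restricts the primary analysis to recent tests, Section 11.8 requires complete outcomes, and the main model factors in Section 11.2 are time, place, sex, age and ethnicity.

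Vaccination is recorded with dates, and an analysis by time since vaccination needs them. Mislabelling follows only if status is carried and the dates are ignored or missing. Symptoms are asked for the period since the last visit as well as for the day, and Section 9.1.2 asks for samples and questionnaire on the same day. Both limit the number of swabs without symptom data.

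What does not fall to this defence is the narrowest reading itself. Confined to questionnaire data, the sentence still covers symptoms, self-isolation and contacts, across gaps that its own reason does not justify.

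**Conclusion.** The point holds as a defect of scope, order and justification. Section 11.8 states a positive rule, so this is more than detail left for later, and Section 11.1 rules out a formal analysis plan that would narrow it. Section 11.2 points to an online methods article that is not at hand and might do so.

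The part that can be measured is the gap: nominally 28 to 36 days from v16.0, up to 61 days between consecutive home visits, and up to 92 with one missed visit. These rest on the protocol's windows and a month of 28 to 31 days.

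The resulting bias has no size that the protocol supports. A reader might reach for the 67% lower infection risk in Section 9.6.1 and dilute it by a share of mislabelled vaccinated time. That figure belongs to an antibody level after two vaccinations, not to vaccination status, and no mislabelled share is given. Nor can the 10% non-response in Section 9.4.4 serve as a rate of carried results. It is a planning assumption about whole assessment windows, and nothing says that a missed window is filled with an imputed swab.

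**What to change.** Replace the carry sentence in Section 11.8 with a scoped rule:

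- (a) Forward and backward carry only for fixed characteristics, such as sex, ethnicity and date of birth.
- (b) Forward carry only, with a stated maximum gap, for slowly changing items where follow-up asks only for changes, such as occupation, working status, smoking and long-term conditions.
- (c) Vaccination and prior infection status derived from recorded or linked dates, never carried backward. Long COVID likewise should not be carried back before its first report.
- (d) Swab, antibody, symptom, contact and isolation data never carried, and kept complete-case. The look-backs in Section 6 stay as outcome definitions.
- (e) The permitted carry first, the complete-case restriction second.

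The reference to short time scales should go, or be limited to the weekly phase.

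The cost is one paragraph, a change in derivation code and slightly fewer records in some models. Keeping (b) matters: limiting all carry to fixed characteristics would leave blanks wherever a participant simply had no change to report.

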Initial sampling for recruitment will be stratified by geographical location in order to provide more precise regional estimates of incidence and seroprevalence. Where possible, sampling will also be stratified by ethnicity to ensure sufficient numbers for appropriate representation in final weighted estimates of prevalence. From Phase II, sampling may be proportionately increased in regions or occupations or other groups with any evidence of increasing prevalence, in order to provide greater certainty regarding the probability of increasing infection rates as opposed to sampling variation. Sampling will also take into consideration local non-response rates to ensure those recruited remain regionally representative as much as possible. Those approached to provide blood samples from enrolment were selected completely at random from the initial recruitment invitation letters. To ensure that the expanded cohort providing blood samples is representative of the different regions, has the greatest possible power to investigate the impact of ethnicity, and places the least burden on participants, invitations to households to join the blood cohort after recruitment will be randomly selected stratified by sub-regional geographical area, but proportionately increased in households where anyone reports coming from an ethnic group other than White. Only households where anyone originally consented to repeated follow-up for longer than one month will be approached for consent for additional blood sampling. Sampling will also be proportionately adjusted to take into consideration nonresponse rates to the invitation to provide additional blood samples by factors including sub-region and age, to ensure those providing blood samples remain representative as much as possible.

Table 1 Original planned recruitment of households in England* +

[figure not shown]
	Newly recruited households in	Newly recruited individuals
	England (actual or approx	in England (actual or approx
Week starting	planned)	planned)
27 April 2020	2523	5483
•	3156	7038
04 May 2020		
11 May 2020	2436	5406
18 May 2020	1365	3092
25 May 2020	442	999
01 June 2020	1163	2526
08 June 2020	2008	4207
15 June 2020	2261	4550
22 June 2020	1778	3622
29 June 2020	1645	3469
06 July 2020	1598	3244
13 July 2020	2500	5388
20 July 2020	2500	5388
27 July 2020	3000	6466
03 August 2020	5000	10776
10 August 2020	7500	16164
17 August 2020	8250	17780
24 August 2020	9000	19397
31 August 2020	9000	19397

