9.1. Recruitment

Households will be recruited from databases of addresses (Phase II) and existing and ongoing ONS and NISRA surveys, including the ONS Opinions COVID-19 Survey in Phase I. This survey is wave 6 of the Labour Force Survey and recruits one adult per household across the UK to ask non-medical questions about the impact of SARS-CoV-2. The survey is voluntary and is conducted in compliance with the Code of Practice for Official Statistics. As part of this survey, participants indicate whether they are happy to be approached for future research and those who have indicated that they are willing will be approached for recruitment into Phase I of this study.

As of 18 April 2020, approximately 5,000 adults from across the UK have agreed to be approached for future research from this survey. Phase I will approach all these adults in England for feasibility reasons relating to initial availability of study workers, together with other households identified from the Labour Force Survey who have similarly agreed to be approached for future research. Recruitment into the Opinions COVID-19 Survey is continuing, with approximately 4,000 adults being recruited per month for at least May and June 2020. Given its size and scale, Phase II will extend this approach to sampling, by continuing to recruit individuals who have indicated that they are willing to be approached about future studies from other ONS and NISRA surveys and also include participants in the Devolved Administrations, and also by selecting households randomly from a commercially available source such as AddressBase, which is maintained by the Ordnance Survey, or equivalent databases including in the Devolved Administrations. This will ensure that the sample remains representative in terms of the country throughout its duration and also facilitate proportionate increases where there is evidence of increasing prevalence.

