The required reduction in sample size and transition to the new approach to delivery from 1 April 2022 will be achieved as follows. First, all participants will be informed that from 1 April 2022, the compensation vouchers will reduce from £25 to £20 per assessment, and that, if they prefer not to continue the study, they should contact the contact centre to withdraw. The numbers choosing to withdraw are unknown, but could be 5-25%. Depending on this, up to 20% of existing participants will be contacted in April 2022 to thank them for their participation and explain that the study has a reduced sample size and it will no longer be possible to continue to include them. Priority will be given to retaining participants with under-represented characteristics, including non-White ethnicity, higher deprivation, smaller household sizes, giving blood by fingerprick and with longest participation and fewest missed visits in the study wherever possible, to improve overall representativeness and maximise the value of the most complete histories of SARS-CoV-2 infections to meet objectives.

Remaining participants will be invited to transition to the new approach to delivery in four stages. Stages 2-4 form a randomised stepped wedge design, enabling statistical comparisons to be made between

answers to questionnaires administered by study workers or online/over the telephone, and swabs/bloods returned by different mechanisms, and ensuring that the study retains sufficient numbers under plausible assumptions to continue to report on positivity (see below).

- Stage 1 (target start date for opt in invitations 21 March 2022²) is a small scale transition of up to 2,000 households, sampled purposively to capture the experience of a range of ages, ethnicities, deprivation, household size and reported long-term health conditions, in transitioning to the new approach. All participants in Stage 1 will be asked to provide feedback on their experience of the new arrangements in order to improve logistics through short surveys; a purposively selected sub-sample will be invited to qualitative interviews (see Section 9.4.4.1 below for details). CDDO term this small scale initial transition the "private beta". CDDO approval is required to proceed to Stage 2.

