Assuming that 90% of participants respond to the initial communication, increasing to 99% after the 20-40 day reminder, that ultimately 81% of participants chose to transition to the new format (increasing gradually predominantly over the 6 weeks from the initial communication), that 90% respond in any given assessment window, that individual assessment window non-response is 10%, that overall 97% of sample kits posted that are returned are done so a median 7 days after the start of each assessment window, this staged approach would lead to the number of completed swab tests shown below in Figure 4 over weeks from start of Stage 2, assuming that a theoretical 100,000 participants are currently visited each week (approximately the case). If a greater percentage chose to continue in the study, then the final numbers will be higher, but the trends will be similar. As the percentages who will choose to continue are unknown, randomisation will be stratified, with households with under-represented characteristics, longest participation and fewest missed visits prioritised for randomisation in Stage 2 and 3, and other participants randomised across Stages 3 and 4. Depending on the percentage who agree to continue, some participants originally planned to be randomised to Stage 4 may need to be contacted to explain that it will no longer be possible to continue to include them, given the reduced sample size.

© Copyright: The University of Oxford and Oxford University Hospitals NHS Foundation Trust 2019 Page 52 of 113

² All dates are indicative targets, depending on approval from the Research Ethics Committee, completion of the database for online/telephone questionnaire completion, and, for later stages, approval from CDDO and absence of need to make other changes based on participant feedback.

Clinical Research Protocol Template version 15.0

During each of Stages 2, 3 and 4, adjusted estimates of swab and antibody positivity (adjusting for sex, age, ethnicity and region as used in the post-stratification (see Section 11.2), and also further adjusting for deprivation and household size) would be compared between those randomised to transition to the new approach to delivery and returning swab tests and those randomised to still receive study worker visits. This, together with analyses of response rates by these factors, will enable an assessment of whether future adjustments for response rates are necessary.

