11.2. Description of the Statistical Methods

For the primary outcome, Bayesian dynamic spatiotemporal multi-level regression with poststratification (MRP) will be used to investigate changes in positivity rates over calendar time.^{25,26} Potential spatial correlation between neighbouring areas is taken into account using a "BYM2" specification. Time will be allowed to vary in a non-linear fashion by using a first-order autoregressive term for time. Space-time, and space-age interactions will be included to allow the positivity over time to vary by age and age group. This spatiotemporal MRP is an extension of the spatial MRP method developed by Gao et al.²⁷ In extensive simulations, Gao et al found that bias was significantly reduced when using a BYM2 specification compared to a non-spatial independent identically distributed specification. Attenuation in absolute bias was most apparent with small sample sizes. Even when simulating outcome data as a multivariate independent normal, BYM2 spatial prior produced nearly same posterior estimates as independent identically distributed prior, indicating that the BYM2 spatial prior does not force spatial structure when it is not present.

The reason for using MRP as the primary method is because it allows probabilistic assessment of relatively rapid changes in positivity. MRP consists of two steps. First, a multilevel regression model is used to generate the outcome of interest as a function of (socio)demographic and geographic variables. Next, the resulting outcome estimates for each demographic-geographic respondent type are poststratified by the percentage of each type in the actual overall population. In several empirical and simulation studies MRP was superior at both the national and regional levels to classical survey weighted and unweighted approaches, including when using small sample sizes.^{26,28} Factors included in the main models - besides time, space, and a space-time interaction described above – will be sex, age, ethnicity and an age-time interaction. Whether additional interactions are needed will be determined based on the Watanabe-Akaike information criterion.

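### Section 11.8's response weighting was not updated for address-sampled households or for selection after enrolment, so selection within the MRP cells has no specified correction

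*Protocol*

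**What the plan says.** Section 11.1 states that no formal SAP exists, so the protocol text is the plan.

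- **Section 11.8** allows inverse probability weighting or post-stratification to the UK population on three bases. The first is weighting "based on response to the initial ONS letter in adults originally targeted". The second sets those adults beside the people first invited to the source surveys, and the third sets them beside the population at large.
- **Section 11.2** makes MRP the primary method. Besides time, space and their interaction, the factors in the main models "will be sex, age, ethnicity and an age-time interaction". Separate weighted proportions use sampling weights and a weight for non-response to the survey, which is not defined further.
- **Section 9.1** extends Phase II sampling "by selecting households randomly from a commercially available source such as AddressBase", as well as from earlier surveys.
- **Section 9.4.4** allows up to 20% of existing participants to be dropped in April 2022. Priority for staying goes to under-represented groups (non-White ethnicity, higher deprivation, smaller households) and to those "giving blood by fingerprick and with longest participation and fewest missed visits in the study wherever possible". Everyone else is then invited to opt in to postal testing. The planning values are 81% opt-in and 10% non-response per window.
- **Section 9.4.4** also compares positivity, during Stages 2 to 4, between participants randomised to transition who return swabs and those still visited at home. The comparison adjusts for the post-stratification factors plus deprivation and household size. Together with response-rate analyses it "will enable an assessment of whether future adjustments for response rates are necessary".

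**The concern.** The response term in section 11.8 describes how people entered Phase I: one known adult per household, drawn from a previous survey, answering one letter. The sample from April 2022 is shaped by later steps, some of them deliberate choices by the study on variables outside the main model. Section 11.8 was revised for the postal phase, since it now says that missing data may increase, but its weighting sentence was left as it was.

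The primary objective is prevalence over time. If people who remain and return swabs differ in infection risk from those who do not, within the same sex, age, ethnicity and area, the series could move at the transition for reasons unrelated to the epidemic. Sampling intervals would not show this, because they do not reflect selection.

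**Working it through.** **1. Do the bases in 11.8 fit the current sample?**
For a household drawn from an address database, section 9.1 gives the household as a whole as the point of contact, and any member may join. Section 9.6.1 confirms that prior-survey occupation is not held for people found through address lists. So the first basis has no targeted adult and the second has no prior-survey invitee. The third basis, comparison with the UK population, still works, including for children.

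**2. Where is each selection step corrected?**

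| Step | Selection variables | Correction stated |
|---|---|---|
| First invitation | response of the targeted adult | 11.8 |
| Retention, April 2022 | ethnicity, deprivation, household size, blood-giving, participation length, missed visits | MRP covers ethnicity; none named for the rest |
| Opt-in to postal testing | not fixed by design | MRP cells; anything further is conditional (9.4.4) |
| Window non-response | not fixed by design | MRP cells; anything further is conditional (9.4.4) |

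**3. What does post-stratification correct?**
Take two equal cells with assumed positivity 2% and 4% and response 90% and 55.8% (mean 72.9%).
- Truth: 0.5 × 2% + 0.5 × 4% = 3.00%.
- Unweighted: (0.5 × 0.02 × 0.90 + 0.5 × 0.04 × 0.558) / 0.729 = 2.77%.
- Post-stratified: 3.00%.

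Attrition that runs through the cells is removed at whatever stage it occurs. Only selection within cells remains.

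**4. Does the stage comparison close the gap?**
Section 9.4.4 puts under-represented households and those with long participation and few missed visits preferentially into Stages 2 and 3. Other participants go to Stages 3 and 4. The adjusters include deprivation and household size but not adherence, so the two arms can differ on a variable that drives allocation. People dropped beforehand are in neither arm. After Stage 4 no home-visit group remains.

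**5. How large could it be?**
The protocol gives no bias figure to reproduce. Its planning values give the share observed, f:
- 0.81 × 0.90 = 72.9%.
- If the 97% kit figure is read as a return rate (the wording is unclear): 0.729 × 0.97 = 70.7%.
- If the full 20% is also removed first: 0.80 × 0.707 = 56.6%.

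Let R be the ratio of positivity in the unobserved to the observed. R is assumed; the protocol gives none. Then true prevalence = p × [f + (1 − f) × R]. Section 11.3 mentions infection rates above 3%, so p = 3% is used.

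| R (assumed) | f = 72.9% | f = 56.6% |
|---|---|---|
| 0.8 | 2.84% | 2.74% |
| 1.0 | 3.00% | 3.00% |
| 1.25 | 3.20% | 3.33% |

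For scale, the simple binomial 95% half-width in England is 1.96 × √(0.03 × 0.97 / 227,300) = 0.07 points per 28 days, and 0.10 points per fortnight with half that number. Household clustering would widen both.

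**The case against.** The strongest reply is that the initial-letter clause does not govern the primary analysis. MRP does, and step 3 shows that it removes later attrition running through its factors. Section 11.8 also allows post-stratification, which needs no targeted adult, and section 11.2 weights for non-response to the survey without limiting this to the first letter. Retention priority goes to under-represented groups too, which may improve representativeness. Stages 2 to 4 are randomised, and response rates are to be analysed. Section 11.2 refers to an external methods article that may say more, and section 11.9 requires deviations to be justified.

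Most of this stands. It rules out a reading that section 11.8 might invite: that only first-letter response is modelled, so everything later goes uncorrected.

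What it does not supply is a correction for selection within cells. The non-response weight in 11.2 is undefined, and the only response term spelled out is the one in 11.8. The stage comparison omits adherence, and further adjustment depends on its outcome. An external article that is not part of the plan cannot repair a sentence that no longer describes the sample.

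**Conclusion.** The stated weighting rule does not match the current sample. Within the MRP cells, no correction is specified for selection on deprivation, household size, blood-giving, participation length or missed visits, or for any remaining selection through opt-in and window response. This is a gap in specification, not a demonstrated bias.

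A reader might infer from the April 2022 rules that prevalence is understated. The documents do not support that. Ratios below 1 reverse the sign and a ratio of 1 gives no bias. The range of 2.74% to 3.33% rests on assumed ratios, on planning values rather than observed rates, and at its extremes on full use of the 20% removal. It is also calculated before MRP removes its share, so it is not the bias of the planned estimator. Nor is all of the loss new, because visits could already be missed under home visiting. The range shows only that modest differences within cells could exceed the sampling error.

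**What to change.** Three changes to the text:

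1. **Section 11.8, weighted proportions.** Replace the initial-letter clause with household selection probabilities multiplied by a retention and response model for enrolled participants. Predictors: demographics, deprivation, household size, time in study, past missed visits, blood-cohort status and transition stage. Calibrate the result to the UK population, and state that this is the non-response weight meant in section 11.2.
2. **Section 11.2, MRP.** From April 2022, run the model with deprivation and household size added as a standing sensitivity analysis. Section 9.4.4 already uses both as adjusters.
3. **Section 9.4.4, stage comparison.** Adjust for the randomisation strata, including participation length and missed visits. State that the comparison does not cover participants dropped beforehand.

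The retention and staging rules already rely on most of these predictors, so little or no new data collection should be needed. The cost is more analysis work and somewhat wider intervals from more variable weights.
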